Study Implementation and Data Security. We will take careful precautions to maintain confidentiality for all participants, using procedures we have used with similar previous studies: All research personnel will attend a required in-service training conducted by PI where the screening, informed consent, and assessment protocols will be described. All members of the research team will sign a confidentiality agreement that no identifying information of specific individuals will appear in any external documents (e.g., peer-reviewed publications, presentations) or in any internal reports.

All study data related to psychological outcomes (i.e., the participant responses to questionnaires) and demographics will not have any unique identifying data attached in any way. All participants will be assigned a numerical study identifier to minimize the potential to link identifying information with study data. One master list of study participants will be kept separate from all other study data. The master list will be destroyed upon study completion; it will be kept separate from all data and will be available only to the PI, Study Coordinator, and research assistants. To protect participant confidentiality, all data will be maintained in a manner consistent with IRB-approved protocol. Data will be stored in locked filing cabinets within a locked office and on MUSC's encrypted computers and data servers. Access to de-identified study data will be limited to named project investigators, the Study Coordinator, NIH audit personnel, MUSC IRB audit personnel, and the VAMC Office of Research & Development (R&D) personnel. Data will be maintained per an IRB-approved protocol.

The study protocol and safety plan will be printed and kept in a central location within the research space for easy access for all research staff. Standard operating procedures (SOPs) for the management of any participant or study-related emergency will be established and research staff will be trained on these protocols. At least two members of the study team will be present during all participant appointments in order to ensure the safety of participants and research staff. Appointments will be scheduled primarily during normal working hours, however accommodations will be made to fit participants' schedules.

All research staff has completed or will complete the University of Miami CITI training course in the responsible conduct of research. Necessary certifications in the responsible conduct of research and the protection of human research participants will be completed on an annual basis, in compliance with MUSC institutional and NIH regulations.

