### *AUD Symptom Severity*

- **Time Line Follow-[name] (TLFB):** The TLFB, which uses a calendar to stimulate recall, will assess consumption of alcohol (e.g., number of standard drink units, percent of days drinking and abstinence, time span in which drinks were consumed), drugs, and tobacco for 60 days prior to study entry, and during the treatment and follow-up phase.

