## **5.0 Number of Subjects**

100 couples will be enrolled (200 total participants).

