## 11.0 Data Management and Statistical Analysis Plan

**General.** Baseline clinical and descriptive characteristics will be examined and compared between treatment groups using chi-square tests, Fisher's exact tests, t-tests, or Wilcoxon rank sum tests, as appropriate. Baseline characteristics that are significantly different between treatment groups will be included as model covariates. The primary analysis will focus on end-of-treatment (i.e., the final three weeks of the treatment phase) outcomes using an intent-to-treat framework.

**Randomization.** Both partners in each couple will be randomized to the same drug condition in a one-to-one manner utilizing a randomized permuted block design. In order to ensure that the treatment groups are balanced with respect to alcohol consumption (TLFB), a stratified randomization process will be used.

We plan to use REDCap and VA REDCap for data capture and management. REDCap (Research Electronic Data Capture) is a software toolset and workflow methodology for electronic collection and management of research and clinical trial data (Harris et al., 2008; Harris et al., 2007). REDCap provides secure, web-based flexible applications, including real time validation rules with automated data type and range checks at the time of entry. Exports are made available for several statistical packages including SPSS, SAS, SATA, R and Microsoft Excel. The system allows the research team to create and engage respondents using a variety of notification methods.

REDCap data dictionaries can be distributed for reuse at multiple institutions. A library of data dictionaries is made available for standards-based data collection forms and validated instruments (Obeid et al., 2012). The underlying database is hosted in a secure data center at MUSC/VA, a secure environment for data systems and servers on campus, and includes redundancy, failover capability, backups and extensive security checks. The system has several layers of protection including, user/group account management, "Data Access Groups" which allow data to be entered by multiple groups in one database with segmented user rights for entered data, audit trails for all changes, queries and reports, and Secure Sockets Layer (SSL) encryption.

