**Power and Sample Size.** This study is powered to detect moderate treatment group differences in percent days abstinent (PDA) and percent of days of heavy drinking (PDH), and relationship functioning as measured by the TLFB and DAS-7, respectively at end-of-treatment (weeks 9-12). Assuming 2-sided hypothesis testing and alpha levels of 0.05, we will have 80% power to detect treatment group differences with effect sizes of 0.6 in the presence of 30% attrition (n=70 couples) during the treatment phase. This approach is consistent with treatment group differences in PDA ( $d=0.59$ ) and PDH improvements ( $d=0.79$ ) in a prior ABCT trial (n=102), although we recognize that that trial compared individual therapy vs. ABCT (not ABCT  $\pm$  medication). In that study, PDA increased from  $34.98\% \pm 29.17\%$  to  $80.52\% \pm 27.75\%$  at the end of treatment in the ABCT group, and PDH decreased from  $56.83\% \pm 28.87\%$  to  $10.52\% \pm 22.16\%$  in the ABCT group. Incorporating an arcsine or other appropriate transformation to account for non-normality of these metrics will enable us to discern whether oxytocin enhances end of treatment PDA by an additional absolute 9% or greater (i.e., to 80.5% in the ABCT+ placebo group vs. 89.5% in the ABCT + oxytocin group) and whether oxytocin further decreases PDH by an absolute 6% or greater (i.e., to 10.5%

in the ABCT+ placebo group vs. 4.5% in the ABCT + oxytocin group). Another prior ABCT trial found that DAS-7 scores ( $21.1 \pm 6.7$ ) remain relatively constant throughout treatment. We will have 80% power to detect treatment group differences of 4 units of improvement in DAS-7 scores.

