In the event that a participant becomes distressed secondary to participation, they will be encouraged to contact the PI. In addition, they will have access to urgent care services at MUSC and VAMC treatment clinics, as well as the VA Crisis Line. Telehealth participants not located in Charleston will be provided with urgent care contact information local to them. Any adverse effects noted by any project personnel will be immediately reported to the PIs, who will then report these adverse effects in writing to the IRB and NIH per protocol (see the Data and Safety Monitoring Plan at the end of this section for more details). The research team includes several licensed clinical psychologists and psychiatrists who are equipped to help

participants manage distress and to evaluate conditions in which participants need additional assistance. In the event that a participant becomes significantly distressed, the PI will contact the participant later that day to check-in and the following day to ensure they have received necessary resources, and to assess their safety and welfare. If called by participants, the PI will attempt to address all participant concerns and set up an alternate referral for counseling for those who desire it from outside the project.

Every attempt will be made to engage participants for the duration of the 12-session treatment phase. Participants will be considered drop-outs from the treatment phase if they fail to attend therapy sessions for four consecutive weeks, in spite of attempts by phone, email and mail to engage the participant in treatment. All telehealth participants complete a participant locator form prior to each visit, that allows the study team to identify local emergency care facilities and contact information. Specifically, for out of state or remote participants, the study staff will compile a list of referrals and emergency contacts to provide to study participants ahead of enrollment. Participants will be provided with contact information for their local mental health clinicians, urgent care, and national suicide prevention lifeline for their use should suicidal ideation occur outside of weekly therapy sessions. Should a suicide safety plan be needed based on participant's BDI during either baseline or weekly visits, participants will meet with study therapist to complete the suicide safety plan together which will also include resources which are local to the participant.

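### The plan makes no provision for collecting end-of-treatment TLFB and DAS-7 from couples who stop attending therapy, although the analysis is intent-to-treat and remote collection is feasible

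*Combined protocol and SAP*

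**What the plan says.** **Drop-out.** Section 14.0 (Adequacy of Protection against Risks, Assessment Procedures) states: "Participants will be considered drop-outs from the treatment phase if they fail to attend therapy sessions for four consecutive weeks". The phone, email and mail contact described there is meant to bring the person back to treatment. Collecting outcomes is not mentioned.

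**Power.** Section 11.0 (Power and Sample Size) claims 80% power for an effect size of 0.6 "in the presence of 30% attrition (n=70 couples) during the treatment phase".

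**Analysis.** Section 11.0 (General) specifies end-of-treatment "outcomes using an intent-to-treat framework". It defines end of treatment as the last three weeks of treatment, while the power paragraph and the model for Hypotheses 1 and 2 use weeks 9-12. The Missing Data paragraph argues that randomization makes bias from missing data unlikely. It adds multiple imputation when more than 10% is missing, to examine the influence of the missing data.

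**Measurement.** Section 3.0 has the TLFB cover alcohol use "for 60 days prior to study entry, and during the treatment and follow-up phase". The DAS-7 is a seven-item self-report. Table 1 lists both weekly and again in separate week 6, week 12, 3-month and 6-month columns. Section 6.0 and Section 9.0 (Telehealth) allow remote procedures.

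**Payment.** Section 9.0 (Compensation) pays for baseline, weekly therapy sessions, follow-up visits and the optional imaging. It has no separate payment for a week-12 outcome assessment.

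**The concern.** Stopping therapy does not by itself prevent measurement. An intent-to-treat comparison needs the end-of-treatment values of everyone randomized, including those who left therapy. The plan defines leaving by therapy attendance, directs its contact attempts at treatment, and sizes the study as though leaving treatment and lacking an endpoint were the same. Staff who follow the text have no instruction to seek the endpoint from a couple who stopped in, say, week 5.

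This matters because drop-out in an alcohol trial plausibly tracks relapse and relationship distress, and may differ by arm. Randomization balances baseline characteristics. It does not protect against selective loss afterwards, so the reassurance in the Missing Data paragraph does not cover this case. Imputation has to infer from other participants what a short contact might have observed. At the assumed 30%, three times the plan's own 10% trigger, the primary result would lean heavily on that inference.

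**Working it through.** **Inputs.** All are from Section 11.0 unless noted.
- 100 couples enrolled (Section 5.0), allocated 1:1 by couple.
- 30% attrition: 100 × (1 − 0.30) = 70 couples, 35 per arm. This reproduces.
- d = 0.6. The test level is "Assuming 2-sided hypothesis testing and alpha levels of 0.05".

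**The plan's own power figure.** For a two-sample t test with n per arm, the noncentrality is d × √(n/2) on 2n − 2 degrees of freedom.
- n = 35: 0.6 × √17.5 = 2.51 on 68 df, giving power 69.7%. The normal approximation gives Φ(2.51 − 1.96) = 70.9%.
- The stated 80% is not reproduced. A two-sided t test needs 45 per arm (90 couples, 80.4%). A one-sided 0.05 calculation gives 35 per arm, but the text says two-sided. Baseline adjustment would reach 80% at a baseline-outcome correlation of about 0.47, but no correlation is stated.

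The comparison below therefore starts from 69.7%.

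**Adding endpoint data.** The documents give no recoverable share, so it is varied as an assumption. This table supposes that recovered couples show the full effect.

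| Share of 30 recovered | Couples analysed | Power (t test) |
|---|---|---|
| 0% | 70 | 69.7% |
| 25% | 77.5 | 74.1% |
| 50% | 85 | 78.1% |
| 75% | 92.5 | 81.5% |
| 100% | 100 | 84.4% |

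**Allowing for dilution.** Couples who stopped drug and therapy may show less effect. If a fraction f of the effect remains in R recovered couples, split equally between arms and with unchanged SD, then d = 0.6 × (70 + R × f) / (70 + R).

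| R | f = 0 | f = 0.5 | f = 1 |
|---|---|---|---|
| 15 | d = 0.494, 61.5% | d = 0.547, 70.3% | d = 0.600, 78.1% |
| 30 | d = 0.420, 54.8% | d = 0.510, 71.4% | d = 0.600, 84.4% |

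At half effect, recovery leaves power almost unchanged (69.7% to 70.3% or 71.4%). With no effect in the recovered couples, power falls. Power is therefore not the main argument for collecting these data. The smaller d in the diluted rows is the intent-to-treat effect itself, which an analysis of 70 attenders would not estimate.

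**Recall.** A contact at week 12 looks back 21 days (final three weeks) or 28 days (weeks 9-12). Both are under half of the 60 days used at entry. If the 3-month visit is counted from the end of treatment (an assumption), weeks 9-12 then lie about 90 days back at the near end and 90 + 28 = 118 days at the far end, beyond the 60-day precedent. The DAS-7 is not a calendar measure. A week-12 contact yields one value at that contact, and a 3-month visit yields no end-of-treatment value.

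**The case against.** The strongest reply is that the documents never exclude these couples. The drop-out rule concerns the treatment phase only. The analysis is intent-to-treat, imputation is planned, Table 1 has a week-12 column separate from the weekly one, and the 3- and 6-month visits are not limited to completers. Section 12.0 (Study Safety) keeps following a participant who becomes pregnant and stops study drug, and cites intent-to-treat in letting her continue therapy. A TLFB at 3 months could already reach back over the treatment phase. All of this is fair. A reader might infer that non-attenders are written off from the endpoint, but the text does not support that. What remains is that no sentence tells staff to seek end-of-treatment outcomes once therapy stops, while the power paragraph counts 30 couples as lost.

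The second reply is that these people have already failed to return despite phone, email and mail contact, and that the 30% may include voluntary withdrawals (Section 13.0) and removals under the Safety and Monitoring Plan (Section 14.0). This also stands. A request for data alone may succeed where a request to resume therapy did not, but no figure shows how often. Those who decline would stay missing, probably selectively, so bias would be reduced and not removed.

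**Conclusion.** The gap is real and worth closing: the plan is silent on collecting end-of-treatment TLFB and DAS-7 after therapy stops, and sizes the study as if those data were lost. The main gain is less bias in the intent-to-treat estimate. That rests on the judgement, plausible but not documented, that drop-out is related to drinking.

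Two stronger readings should be resisted. One is that much of the 30% loss is avoidable with a single call. The recoverable share is unknown. The other is that power would rise by some 8 points (69.7% to 78.1%) with half of the lost couples recovered. That holds only if they show the full d = 0.6. With half the effect, power is 70.3%; with none, 61.5%. All these figures are for an unadjusted two-sided t test with recovered couples split equally between arms.

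**What to change.** 1. Reconcile the end-of-treatment window in Section 11.0 (final three weeks in General; weeks 9-12 in Power and Sample Size and in the model for Hypotheses 1 and 2).
2. Add after the drop-out rule in Section 14.0: *Stopping therapy or study drug does not end outcome assessment. Each partner who has stopped attending and has not withdrawn consent is contacted by phone or video at week 12 to complete the alcohol TLFB for the end-of-treatment window and one DAS-7.* The rules for withdrawing participants are left as they stand.
3. State that TLFB data for those days obtained only at the 3-month visit are used as sensitivity data, because recall may exceed 60 days, and that this visit supplies no end-of-treatment DAS-7.
4. In Power and Sample Size, give attrition from therapy and assumed loss of endpoint data as two separate figures.

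**Cost.** One short contact per non-attending partner by existing staff, and a few sentences of text. Including couples who stopped treatment may also dilute the observed effect; the sample size reasoning should say so.

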Exclusion criteria include: 1) meeting DSM-5 criteria for a history of or current psychotic or bipolar affective disorders, 2) current suicidal or homicidal ideation and intent, 3) a history of seizures and/or a seizure disorder per the judgement of the medical clinician, 4) severe, unilateral intimate partner violence in the past 6 months as defined by the Revised Conflict Tactics Scale, and 5) pregnancy or breastfeeding for women, 6) Acute alcohol withdrawal as indicated by CIWA-Ar scores  $>8$ , Attendance at therapeutic activities other than study sessions will be closely monitored using the Treatment Services Review, 7) any unstable or serious medical condition affecting the potential participant's ability to participate in the study, 8) Individuals with claustrophobia; tattoos above the shoulders; permanent eyeliner or permanent artificial eyebrows; cardiac pacemaker; metal fragments in eye, skin, or body, including shrapnel; heart valve replacement; brain clips; venous umbrella; current or former sheet-metal worker or welder; lifetime history of aneurysm surgery; lifetime history of seizures and/or epilepsy per the judgement of the medical clinician; intracranial bypass, renal, or aortic clips; prosthetic devices such as middle ear, eye, joint, or penile implants; joint replacements; non-removable hearing aid, neurostimulator, or insulin pump; shunts/stents; metal mesh/coil implants; metal plate/pin/screws/wires; or any other MRI contraindications as determined by the MRI technician at the time of scanning will not be eligible to participate in the neuroimaging component of the study, however individuals who meet inclusion/exclusion criteria for the medication component of the study but not the MRI portion will still be eligible to reenroll in and complete the medication/treatment phase.

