#### *Exclusion criteria*

- 1) Meeting DSM-5 criteria for a history of or current psychotic or bipolar affective disorders, or with current suicidal or homicidal ideation and intent. Those individuals will be referred clinically for treatment.
- 2) Participants who present a serious suicide risk or are likely to require hospitalization during the study.
- 3) Participants on psychotropic medications which have been initiated during the past 4 weeks. They may be re-assessed after at least four weeks on a stable dose.

- 4) Acute alcohol withdrawal as indicated by CIWA-Ar scores >8. They may be re-assessed once they are no longer in withdrawal. Those individuals will be referred for medically supervised detoxification.
- 5) Severe unilateral intimate partner violence in the past 6 months as defined by the CTS-2.
- 6) Pregnancy or breastfeeding for women.
- 7) Individuals with implanted metal devices above the waist will be eligible to enroll in the clinical trial but will not be eligible to participate in the neuroimaging component of the study.

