Safety and Monitoring Plan. A procedure for clinical deterioration has been established based upon our experience with previous and ongoing NIH-funded clinical trials. Therapists (who will be trained Master's or Doctoral level clinicians) will be instructed to use their best clinical judgment regarding emergencies and inform the PI as soon as possible. In addition to relying on clinical judgment on the part of the treating therapists who are experienced with this population, we will also monitor alcohol and drug use, depression, and relationship functioning weekly using standardized measures (TLFB, BDI-II, DAS-7, breathalyzer/saliva alcohol tests) in order to detect any symptom worsening requiring further evaluation. Additionally, participants will be advised to observe any signs of worsening alcohol use, depression symptoms, or relationship functioning including intimate partner violence, and to discuss these challenges with their therapist.

Participants will be withdrawn from the study and referred for more intensive treatment if: (1) there are increases in alcohol use leading to the need for a more intensive level of care (i.e., medical detoxification, inpatient or partial hospitalization); (2) there is active suicidal or homicidal ideation and/or intent; (3) there is an inability to manage the participant psychiatrically within the inclusion/exclusion criteria of the study (i.e., need for the initiation of psychotropic medications; development of psychosis); or (4) there is an inability to complete ABCT therapy appointments due to incarceration or hospitalization.

There is a well-established protocol at MUSC for emergency psychiatric evaluation, crisis intervention and/or psychiatric hospitalization for suicidal, homicidal, psychotic or other acutely distressed participants. Immediately on detection of these needs, the assessor/therapist will page a psychiatrist to review the participant's situation. If appropriate, the psychiatrist will personally evaluate the participant. Alternatively, during weekdays, the participant will be escorted by a study staff member to the psychiatric walk-in clinic or emergency room. Psychiatric hospitalization is available for emergencies.

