Suicide Specific Risk Identification and Response Plan. Specific precautions will be taken to prevent harm to participants and potential participants. Project therapists will be trained Masters or Doctorate level clinicians and will be supervised by [name] (PI) and [name] (Co-I), who are licensed clinical psychologists. All project therapists and staff will be specifically trained to assess suicide risk, including ideation, plan, and intent as well as history of ideation or attempts, and they will be trained to develop a safety plan with participants. In initial screening procedures, participants identified by clinical interview with both suicidal ideation and acute intent will be excluded from the study, but will be offered emergency psychiatric care immediately. This care is available 24 hours per day at MUSC and the Charleston VAMC, as indicated above. Moreover, during the course of the study, any participant scoring above 25 on the BDI-II (administered weekly) or answering a 1 or above to question 9 will be specifically queried about suicidal ideation and intent. In any instance where ideation or intent is identified, the PI will be immediately notified and will contact the participant for further evaluation. If both ideation and intent are present, the aforementioned hospital intervention will be provided. Thus, all assessment points represent suicide risk identification, assessment, and intervention opportunities. Study therapists and staff will be specifically trained regarding the increased risk of suicide in Veterans with chronic pain and substance use disorders, and will receive specific instruction of suicide risk assessment during the initial training workshop. In the case of acutely suicidal or distressed veterans participating via telehealth and located outside of our immediate geographical location (and the state of South Carolina), the study team will initiate a three-way call with the VA Veteran Crisis Line who has the ability to locate the veteran and send emergency help to the veteran.

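### A person with active suicidal or homicidal ideation but no intent can pass the entry criteria and at the same time meet a compulsory withdrawal rule

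*Combined protocol and SAP*

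**What the plan says.** **At entry.** Section 4.0 lists as an exclusion "current suicidal or homicidal ideation and intent". The first item of the exclusion list in Section 12.0 repeats the conjunction: "or with current suicidal or homicidal ideation and intent". The Suicide Specific Risk Identification and Response Plan in Section 14.0 puts it most plainly, for suicide only: "participants identified by clinical interview with both suicidal ideation and acute intent will be excluded from the study". Section 12.0, but not Section 4.0, adds a further exclusion: "Participants who present a serious suicide risk or are likely to require hospitalization during the study".

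**Withdrawal.** The Safety and Monitoring Plan in Section 14.0 opens its list with "Participants will be withdrawn from the study and referred for more intensive treatment if". Its second item is "there is active suicidal or homicidal ideation and/or intent". Section 13.0 has a separate provision under which the principal investigator may end participation when someone presents a risk of harm to self or others.

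**Response during the study.** The suicide-risk plan says: "In any instance where ideation or intent is identified, the PI will be immediately notified and will contact the participant for further evaluation". It reserves the hospital route for cases where ideation and intent are both present. The Assessment Procedures part of Section 14.0 has the participant and the study therapist write a safety plan together: "Should a suicide safety plan be needed based on participant's BDI during either baseline or weekly visits". The Military Personnel paragraph also asks for a safety plan when a participant reports a risk of harm to self or others. None of these three places mentions withdrawal.

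**The concern.** The entry test and the withdrawal test use different logic for the same clinical state. Entry needs ideation and intent together. Withdrawal needs either one, and it is compulsory. A participant can then be correctly enrolled under one section and required to leave under another, with no change in condition.

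Two things are at stake. The first is a safety instruction that staff cannot apply consistently: two assessors seeing the same participant could retain or withdraw, and each could point to a section in support. The second is who remains in the trial after randomisation. Section 11.0 plans an intent-to-treat analysis of end-of-treatment outcomes. The documents do not say whether a person withdrawn under this rule still provides those outcomes. If not, the rule removes outcome data for a state that the entry criteria permit.

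**Working it through.** No arithmetic applies, because the point depends on no rate, alpha, power or sample size. The check sets the entry and withdrawal wording side by side for each combination of ideation and intent.

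1. **Ideation with intent.** Excluded at entry by Sections 4.0 and 12.0 and, for suicide, by the suicide-risk plan. Meets the withdrawal rule. Consistent.
2. **Active ideation without intent.** Not excluded by any of the three entry statements on ideation. Meets the withdrawal rule, because *and/or* makes active ideation sufficient. Contradictory.
3. **Intent without ideation.** The same mismatch on the literal wording, though unlikely in practice.
4. **Ideation that is not active, without intent.** Not excluded at entry and not clearly covered by the withdrawal rule. Where this case ends and case 2 begins depends on *active*, which is not defined. The entry lists use *current*, and the two words are never related to each other.

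Case 2 carries the point. The next question is whether anything else at entry closes it. The serious-suicide-risk exclusion would catch some people with suicidal ideation and no intent. It does not close the case, for three reasons: the term is undefined, it is missing from the Section 4.0 list, and it does not speak to homicidal ideation. A person with active homicidal ideation and no intent is untouched by it.

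Then take the same person when identified during the study. Table 1 schedules the BDI-II at baseline and weekly, and the suicide-risk plan sets a score threshold and an item-9 threshold for specific questioning. From there:

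- the suicide-risk plan leads to notification of, and evaluation by, the principal investigator, with the hospital route only if ideation and intent are both present;
- Assessment Procedures leads to a safety plan at a baseline or weekly visit, so the protocol foresees participants who need one from the outset;
- Section 13.0 leads to a discretionary decision;
- the Safety and Monitoring Plan leads to mandatory withdrawal if the ideation is active.

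No sentence says how the first three connect to the fourth.

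**The case against.** **The withdrawal list is about deterioration.** The Safety and Monitoring Plan opens as a procedure for clinical deterioration. Its first item speaks of increases in alcohol use and its third of developing psychosis. On that view the second item means new or worse ideation, and being eligible and withdrawn on the same day is not the natural reading. This has force as to intention. But the second item says only that active ideation is present and asks for no change from baseline, so the context does not remove the mismatch.

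**The word *active* narrows the trigger.** It does. The rule does not remove everyone with any ideation, and the point is limited to active ideation. Without a definition, *active* cannot separate eligible people from those who must be withdrawn.

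**The conjunction at entry could mean that either state excludes.** The two exclusion lists might be read that way in isolation. The suicide-risk plan's use of *both* rules it out for suicide, and in the lists the same phrase governs suicidal and homicidal ideation alike.

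**The on-study steps can be read in sequence.** Questioning, evaluation, a safety plan, and then withdrawal if the ideation is judged active could all apply to one person. This stands. A reader might infer that the documents give opposite instructions, one to keep the participant and one to remove them. They do not: the safety-plan and evaluation passages are silent on retention. The conflict during the study is between a compulsory rule and a discretionary one, with the link between them unstated.

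**Every route escalates.** Also true. The principal investigator is notified at once, emergency psychiatric assessment is arranged if a participant becomes suicidal, and a psychiatrist can be paged. No route leaves ideation unaddressed. What remains unsettled is enrolment and withdrawal.

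**Conclusion.** Wrong as written: the safety rule is internally contradictory. The conclusion rests on the literal wording of the three entry statements and the withdrawal item. It applies to a person with active ideation, no intent, and no separate judgement of serious suicide risk. Clinical judgement does not resolve it, because the withdrawal list is mandatory and staff are not told which section governs.

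The size cannot be given. A reader might multiply 200 participants by 13 BDI-II occasions (baseline plus 12 weekly) to get 2,600, but that counts questionnaires, not conflicts. A reader might also assume a rate of ideation and set the resulting losses against the planned 30% attrition. The documents give no rate of ideation without intent, still less of active ideation, and do not break the 30% down by cause. Nor does the withdrawal rule say that the partner is withdrawn, so a loss of whole couples cannot be inferred from it. The effect on power is therefore not shown, and the case for changing the text does not depend on it.

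**What to change.** The investigator and the DSMB should reconcile the exclusion lists in Sections 4.0 and 12.0, Section 13.0, and the Assessment Procedures, Military Personnel, Safety and Monitoring Plan and suicide-risk paragraphs of Section 14.0. The amended text should:

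- define *active* and say how it relates to *current*;
- state how a positive weekly screen and the evaluation that follows lead to retention or withdrawal, and whether withdrawal is then compulsory or discretionary;
- ensure that the entry criteria cannot admit a person who already meets a mandatory withdrawal criterion.

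Which clinical rule to adopt is for them to decide. The monitoring trigger and the withdrawal trigger need not be identical, since a screen may reasonably be set lower than the point at which someone is removed.

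The cost is a wording amendment with the usual approval. No new assessment is needed, as the clinical interview and the weekly BDI-II are already scheduled.
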